Our original protocol specified several clinic visit adherence and retention measures that could not be estimated due to unforeseen limitations. Due to missing dates of next appointments in patient charts and variability in 1-month and 2-month prescribing, we were unable to compute "days late for next appointment" or "days without medication", concepts that underpinned two of our three pre-specified retention measures. In lieu of these measures, we defined new, simplified measures to capture longer-run retention concepts. These measures – any ART refills after 30 days; any ART refills during months 1-2, ...months 3-4, and ...months 5-6 – are robust to 1- and 2-month prescribing, and do not rely on accurate recording of future appointment dates.

These changes are indicated in the relevant places below in this protocol and are reflected in the current record at ClinicalTrials.gov (NCT04504357).

5.2.2. Study population and recruitment.

The study population will include adult men and women (18 years and older) receiving routine HIV counseling services at three public sector clinics in Gauteng, South Africa during the study period. Under current standard of care, HIV counseling is provided at two points in time: after an HIV diagnosis (post-test counseling) and after an elevated viral load (adherence counseling). The same counselors provide both services and the study will recruit from both populations, with at least 1/3 from each group. After their visit to the HIV counselor, patients will be referred to study staff for recruitment into the study. Study staff will explain the study, assure the patient that participation is voluntary, and obtain written consent if the patient wishes to enroll. Across the two study phases, we anticipate recruiting a total of n=135 adult men and women receiving HIV counseling services at three public sector clinics in Gauteng, South Africa. (This sample size is feasible – in a prior study we enrolled 600 newly diagnosed PLWH at four clinics in six months.)

Participants who enroll in the study will participate in surveys at enrolment and at 6-months follow-up. The baseline session, including consent (5 min), intake survey (10 min), intervention (if Arm B) (15min), and immediate post-test survey (25 min), is expected to take 45-60 minutes.

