Inclusion / Exclusion: All individuals who receive HIV counseling services, are over 18 years, do not have acute care issues, and are able to consent will be offered enrolment in the study. Patients with acute medical needs who are referred for additional care will not be eligible, so as not to interrupt their care. Patients under 18 years are not eligible. Finally, patients who are not able to consent or who do not consent to participate (including linkage to clinical records) will not be included.

Facility inclusion criteria will be:

- Situated Gauteng province
- Follows national guidelines for viral load monitoring
- HIV positive patient burden≥ 30 per month

Participant inclusion criteria will be:

- Adult patients (>18 years)
- Not pregnant
- (Aim 1) Enrolled in HIV care at study site
- (Aim 2) Received HIV post-test counselling or adherence counselling

Participant exclusion criteria will be:

- Indicates they do not intend to receive HIV care at the study site (Implementation note: this was operationalized as the absence of a clinical chart at the clinic.)
- Requires acute medical care that would be hindered by participation in the study
- Determined by clinical staff not to be physically or emotionally able to initiate ART

- Is currently pregnant
- Does not speak one of the primary study languages: English, Zulu, Sotho, Xhosa
- Is not able to consent (e.g. intoxicated or of limited mental capacity)
- Does not consent to participate in the study, including linkage to clinical records for follow-up of the primary behavioral outcome (ART uptake and adherence over the first 6 months)

5.2.3. Intervention.

The U=U video intervention will be developed in Aim 1. The intervention will be piloted via three treatment modalities: (T1) controlled exposure, using the tablet-based app in the context of a survey; (T2) clinical exposure, in which patients will see the video in the clinic waiting room and will be exposed to the app during HIV counseling; and (T3) text message exposure, with monthly interactive messages.

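### Does applying the stated-intention exclusion as a no-chart check call for a change to the plan?

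*Combined protocol and SAP*

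**What the plan says.** All the eligibility text is in the combined protocol and SAP, section 5.2.2.

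- **Written exclusion:** a patient who "Indicates they do not intend to receive HIV care at the study site".
- **Applied exclusion:** the bracketed remark on the same line, "Implementation note: this was operationalized as the absence of a clinical chart at the clinic". It carries no date.
- **Inclusion by aim:** for the development work, "Aim 1) Enrolled in HIV care at study site"; for the pilot trial, "Aim 2) Received HIV post-test counselling or adherence counselling".
- **Two sources of patients:** counselling is given "after an HIV diagnosis (post-test counseling) and after an elevated viral load (adherence counseling", and recruitment draws on both, "with at least 1/3 from each group".

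Section 5.2.1.1 lists the mid-study changes: the wave 1 contamination, the dropping of Arm C, the lost six-month survey, the viral load window and threshold, and the replacement retention measures. The chart rule is not listed. The section closes its account with "These changes are indicated in the relevant places below in this protocol".

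On sequence, 7.1 places eligibility screening ahead of consent, and 5.2.3.1 places individual randomisation after the intake survey. Section 5.2.6 specifies intention-to-treat analysis, adjusts for clinic and counselling type, and names counselling type as a moderator.

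**The concern.** The two rules can disagree in both directions. A newly diagnosed patient who means to attend the clinic but has no chart there is eligible as written and excluded as applied. That moves the pilot's entry rule towards the in-care requirement listed only for Aim 1. A patient sent to adherence counselling after a raised viral load has been in care already and probably has a chart. If that patient plans to go elsewhere, the written rule excludes and the applied rule may not.

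Two consequences would follow. First, ART uptake is something the trial tries to influence. Screening out post-test patients who never entered care would make uptake look better than it is in the group the criterion describes. Second, planned movers kept in the adherence group would tend to have no refills on record in either arm, pulling a refill difference towards zero on measures such as "any ART refills after 30 days; any ART refills during months 1-2".

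The more serious worry is timing. If charts were looked up after randomisation and people without one were dropped, the exclusion could depend on arm, because engagement in care is what the videos aim to change. That would contradict the intention-to-treat statement. A reader of 5.2.1.1 alone would not learn that the rule had been substituted at all.

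**Working it through.** The plan gives no figure for this rule, so there is none to reproduce beyond the sample counts. Every rate below is an assumption except the one-third minimum and the total of 135.

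**1. Counts (5.2.1, 5.2.1.1, 5.2.2).** Planned: 90 + 45 = 135. Enrolled by wave: 55 + 80 = 135. Analysed: all 135. The totals agree, and no section reports a removal. Agreement is not proof, since replacing dropped participants would give the same total. With at least one third from each group, each group has between 135/3 = 45 and 135 × 2/3 = 90 people.

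**2. Order of events.** Screening, then consent (7.1); intake survey, then randomisation (5.2.3.1). An exclusion criterion applied in that order acts before allocation. Linkage to records needs consent (5.2.2, 5.2.5.4), so the look-up might have followed consent, but consent also precedes randomisation. The text therefore favours a check before randomisation without stating it.

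**3. Adherence group: dilution of a refill difference.** Let w be the adherence share (1/3 to 2/3) and t the share of that group planning care elsewhere. Assume no refill is recorded for any of them in either arm. A 10-point difference then shows as 10 × (1 − w × t).

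| t | people (135 × w × t) | observed difference |
|---|---|---|
| 0.05 | 2.25 to 4.5 | 9.83 to 9.67 |
| 0.10 | 4.5 to 9 | 9.67 to 9.33 |
| 0.20 | 9 to 18 | 9.33 to 8.67 |

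The loss is 0.2 to 1.3 points, in a pilot that 5.2.8 says is not powered for behaviour.

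**4. Post-test group: level of uptake.** Let c be the share without a chart and s their uptake, with 85% uptake among charted patients. Uptake among all counselled is (1 − c) × 0.85 + c × s.

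| c | s = 0 | s = 0.425 | s = 0.85 |
|---|---|---|---|
| 0.10 | 76.5% | 80.8% | 85.0% |
| 0.20 | 68.0% | 76.5% | 85.0% |

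The gap from 85% runs from 0 to 17 points. All counselled patients are not the right comparator, however, because the written rule also excludes those who say they will go elsewhere. If only a share i of the no-chart patients intend care at the site, and charted patients planning care elsewhere are ignored, the gap becomes c × i × (0.85 − s) / (1 − c + c × i). At i = 0 it is zero: the two rules exclude the same no-chart patients. At i = 1 it returns the table, for example 0.20 × 0.85 = 17 points with s = 0. So 17 points requires that every no-chart patient intends care at the site and that none starts ART. The shift is in a level and, under step 2, applies equally to both arms.

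**5. If charts were checked after randomisation.** Assume 80% of Arm A have charts, 60% of these are suppressed, and there is no true effect on suppression. Let Arm B have d more patients charted, with suppression s among the extra ones. A chart-only comparison shows (0.6 × 0.8 + s × d)/(0.8 + d) − 0.6.

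- d = 0.05: −3.5 points at s = 0 and −1.2 at s = 0.4.
- d = 0.10: −6.7 points at s = 0 and −2.2 at s = 0.4.

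This would matter, but no section describes such a removal, and 5.2.6 already requires analysis as randomised.

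**The case for a change.** The best case for acting is that the chart remark alone is both undated and missing from 5.2.1.1. The Arm C remark in 5.2.3 is undated but its change is listed; the text-message remark is unlisted but dated; the other two are dated and listed. Only the sponsor knows when charts were checked, matching totals cannot rule out replacement, and one sentence would settle it. The rule also bears on ART uptake, a quantity the trial studies.

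The facts about the text stand: the rules differ, the list omits the substitution, and the timing is unstated. The further steps do not. No section says when a clinic opens a chart or how many patients lacked one. If a chart is opened at diagnosis or counselling, the excluded post-test group could be empty. An adherence patient's earlier care could have been at another clinic. Nor do the documents say whether staff also asked about care elsewhere. Different selection in the two counselling groups is therefore possible but not shown. The closing statement of 5.2.1.1 says that its listed changes are marked in the text; it does not say that every remark in the text is listed there. The word used, operationalised, describes how an existing criterion was applied.

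**Conclusion.** No change to the plan is needed. This is a disclosed operational rule with a missing reporting detail, and a fair trade-off: a stated intention is hard to verify, a chart can be verified, and the refill outcomes come from clinic records. For the primary viral load outcome, 5.2.5.4 also plans a search of the national laboratory database, which limits the effect of transfers if that search was carried out.

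On the order of events the text favours, there is no between-arm bias and no conflict with intention to treat. On assumed rates, refill dilution is 0.2 to 1.3 points on a 10-point difference. The shift in post-test uptake ranges from nothing to 17 points, the top of that range being implausible, and it affects who is described rather than the arm contrast. Counselling type is already an adjustment variable and a planned moderator, so the split that would reveal any differential selection is already planned.

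The conclusion rests on charts having been checked before randomisation, which is inferred. If that proved wrong, the intention-to-treat rule in 5.2.6 already says how to treat the affected participants. Stating the timing of the check and the number excluded for lack of a chart belongs to ordinary reporting of participant flow.

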5.2.3.1 Intervention assignment, period 1 (two study arms, n=45/arm)

Arm A vs. Arm B. During the first period of recruitment, patients completing HIV post-test or adherence counseling will be referred to study staff for recruitment (Fig 7). Patients will complete a brief intake survey. They will then be randomized 1:1 at the individual level to "no exposure" (Arm A, n=45) vs. "controlled exposure to the tablet-based video intervention" (Arm B, n=45). Arm B will then receive the intervention on tablet, delivered in the study interview setting. Respondents in Arms A and B will then complete additional questions, constituting the immediate post-test survey. Comparisons of outcomes in Arm A and Arm B will enable rigorous inferences on the effect of "controlled exposure" due to randomization.

5.2.3.2 Intervention assignment, period 2 (third study arm, n-45):

Arm C "clinical exposure". We will conduct a demonstration project to assess the feasibility and acceptability of delivering the U=U video intervention in real world clinical settings, rather than in a controlled study context. After period one enrolment has been completed at the three clinics, the intervention will be integrated into routine counseling procedures at each clinic. In collaboration with clinic leadership, HIV counselors will be trained to use the tablet-based U=U intervention to enhance TasP literacy as part of routine counseling and will be provided a tablet for the duration of the pilot. Additionally, the full video intervention will be shown on TVs in the clinic waiting rooms (on repeat, in rotation with other material). All patients receiving counseling at the study clinics after a specified implementation date will be considered "exposed" to the intervention. Patients completing counseling during this period will be referred to study staff for recruitment. Patients who provide consent (Arm C, n=45) will participate in the intake and immediate post test surveys (Fig 7). Comparisons of Arm A and Arm C will enable inferences on the effect of "clinical exposure" to the intervention in a non-randomized pre/post design, comparing patients receiving counseling before and after the intervention at the same facility.

Implementation note: Arm C participants were reallocated to Arms A and B.

5.2.3.4 Text-message reinforcement.

Participants in intervention arms (B-and-C) will additionally be sub-randomized 1:1 to receive six monthly interactive SMS/text messages (for simplicity, not shown in Fig 7) related to the U=U video content. Arm B participants will also receive the App on their phone (if they have a smart phone) and an information sheet, to enable them to continue to engage with the information and share with others.

Implementation note (added 7/30/2025): The six text messages were randomized to enable assessment of impact of different messages. Further, they were delivered on a set schedule (same day each month for all participants) and were not linked to participants next appointment dates. Thus, the text messages were intended to be additional doses of U=U information, not reminders of scheduled clinic visits.

5.2.4. Data collection.

For all study arms, data will be collected on participants via a brief intake survey, an immediate post-test survey conducted during the enrolment visit, a 6-month follow-up survey, and via linkage to clinical records. Fig 7 shows the order of data collection activities for the different study arms. The intake and immediate post-test surveys will be conducted in person on a tablet, with the assistance of a trained interviewer. Due to variable computer literacy in the study population, study staff will be available to assist with reading the survey questions and guiding the participant through the survey. The surveys will be implemented in English, Zulu, and Sotho and Xhosa three of the most widely spoken languages at public sector clinics in Gauteng and Xhosa and English being widely spoken in Western Cape Townships. The 6-month follow-up survey will be conducted in person or by phone for Aim 1 and Aim 2. In addition to these data collection activities, for Arms B and C, participant responses to questions embedded in the App-based intervention and responses to the randomized text messages will be logged.

Implementation note (added 7/30/2025): Six-month survey and Arm C were dropped as described above.

5.2.5. Outcomes and follow-up.

The primary goals of the pilot trial are to establish: (a) feasibility of the intervention and data collection methods; (b) acceptability of the intervention, and different video modules and delivery modalities; (c) effects on knowledge about the efficacy of TasP; (d) effects on attitudes towards ART as a prevention strategy (prevention motivation) and treatment strategy (treatment motivation); and (e) preliminary impact on ART uptake and adherence through six months, defined as the number of monthly ART medication pick-ups over the first six months after study enrolment, as measured in linked clinical records. Additionally, we seek to assess the extent to which effects are moderated by patient characteristics including: gender, age, relationship status, post-test vs. adherence counseling, and altruistic preferences.

5.2.5.1 Intake and immediate post-test survey.

The 10-min intake survey will collect basic information on patient demographics and potential moderators. The 25min post-test survey will include the following domains (described in Aim 1): acceptability of the intervention (Arm B, C), beliefs about the health benefits of ART, beliefs about HIV transmission with / without ART, attitudes towards ART as a prevention strategy, HIV prevention altruism, internalized stigma, mental health, partnership status and towards disclosure, self-efficacy to take ART, barriers to adherence, and self-reported adherence and sexual risk behaviors.

5.2.5.2 Six-month follow-up survey.

The six-month follow-up survey will be conducted at the first scheduled clinic visit occurring after six months since enrolment. Once six months have elapsed, all participants will be contacted with a reminder of their next appointment at the clinic and with a reminder that the follow-up survey will be conducted at that visit. Patients will be given the option of participating in the follow-up survey on another date if more convenient, or by phone. All participants will be compensated for their time participating in the follow-up survey. We will attempt at least three contacts in order to retain respondents for the follow-up interview. The six-month follow-up survey will cover the same domains as the immediate post-test survey.

5.2.5.3. Exit interviews (n=30).

After the six-month follow-up, 30 participants in Arms B and C will be randomly selected to participate in a one-onone, open-ended, key informant interview with study staff. Domains will include: acceptability of the intervention; understanding of information provided; how if at all the intervention affected how they think about ARVs, condoms, sex, and relationships; whether they have talked about TasP with others; and any challenges they have faced due to the intervention. Interviews will be audio recorded, transcribed, translated, and analyzed using a grounded theory approach.⁸⁰ Counselors will also be interviewed to gain their qualitative perspective on the acceptability and feasibility of the intervention.

5.2.5.4. Linkage to clinical records for primary behavioral endpoints.

To assess preliminary impact and to demonstrate feasibility of measuring clinical endpoints, we will link (with consent) to clinical records for six months after study enrolment. Our primary behavioral outcome will be ART uptake and adherence through six months, defined as the number of monthly ART medication disbursements occurring over the six months following study enrolment. Current protocols specify monthly medication pick-ups. Patients may have fewer than six visits if: they did not initiate ART, they delayed initiating ART, they started ART but missed medication pick-ups, or they started but were not retained on ART (or transferred out). Thus, our measure is designed to capture in a single outcome a range of behaviors related to ART uptake and adherence. Because some clinics have moved to same-day ART, we have defined this outcome to be valid regardless of when ART is started. Additionally, the composite measure is likely to have greater power than the individual component measures. As secondary outcomes we will additionally assess ART uptake within 30 days and retention in care at six months, defined as being no more than 30 days late for scheduled clinic visit closest to six months.

We will also assess documented viral suppression at six months. Guidelines specify that a viral load should be conducted at six months after ART initiation. Because patients may take several weeks to initiate ART after diagnosis and because many patients do not get their VL precisely at six months, we will allow for a ten-month window after study enrolment. With consent, we will extract VLs from clinical charts as well as the national laboratory database, enabling us to trace patients who may have transferred to other clinics. We will define suppression as VL<50 copies. We will assess monitoring (regardless of suppression) as a secondary outcome.

Note (added 7/30/2025): changes in behavioral endpoints are described above. Documented VL<200 copies/ml at 3-10 mo was defined as the primary endpoint (due to changes in VL testing guidelines & practices in the middle of the study). Retention measures were adjusted due to missing data on dates of next appointment and variation in 1 vs 2-month ART dispensing.

5.2.6. Data Analysis.

Acceptability will be assessed at immediate post-test with respect to "ease of use" and "usefulness" for intervention study arms (B and C). The intervention will be determined "acceptable" in different subgroups (by moderating variables) if average Likert scores are 3 (out of 4) or higher. We will also assess acceptability, clarity, and salience of specific video modules through embedded questions and rankings in the tablet-based intervention and assessing which were watched again. Other study endpoints will be knowledge and attitudes related to TasP, internalized stigma and mental health, and HIV prevention altruism at immediate post-test and 6 months, and ART uptake and adherence and viral suppression assessed in clinical records. Effects on these endpoints will be assessed through comparisons of study arms. We will conduct separate analyses comparing Arm A ("no exposure") vs Arm B (randomized "controlled exposure"), comparing Arm A ("no exposure") vs Arm C (non-randomized "clinical exposure"), and comparing randomized monthly "text messages" vs. "no text messages" in Arms B and C. For each analysis, treatment arms will be compared across pre-treatment characteristics to assess balance. To evaluate impact, we will compare means for all outcomes across treatment arms using simple linear regression with robust standard errors, adjusting for clinic and type of counselling (stratifying variables). For binary outcomes, we will use logistic regression and estimate marginal effects (risk differences). As a sensitivity analysis, we will adjust for pretreatment characteristics on the intake survey that are substantially imbalanced (p<0.1) and which are thought to be correlated with ART adherence. The trial will be analyzed on an intention-to-treat basis. Every effort will be made to follow up patients for the six-month follow-up survey. Missingness, if >10%, will be addressed via the inverse probability of censoring weights (IPCW). In addition to the "main effects" analyses described, we will assess interactions by theory-driven moderating variables e.g.: counselling type, baseline relationship status, and general altruism.

5.2.7. Sex as a biological variable.

Women and men may engage with the issues surrounding U=U in different ways. We will recruit both men and women to the pilot study. We will assess for gender-specific barriers and facilitators in our qualitative data collection, and we will assess intervention impacts separately by gender. We note that due to the small sample size of this pilot, our primary analyses will pool men and women.

5.2.8. Power.

Our pilot study is powered to detect clinically significant impacts on U=U knowledge and attitudes. In preliminary data, we found that Gauteng university students (n=363) perceived virally-suppressive ART reduced transmission risk by an average of 20% (s.d. 25%). (The actual reduction in risk is at least 96%.) A successful intervention would substantially increase perceived efficacy of ART in reducing transmission. With 45 control participants and 45 treated participants per arm, we are powered at 97% to detect at least a 2-fold increase in perceived efficacy of TasP, from 20% to 40%. This pilot is not powered for impact on behaviors.

5.2.9. Scientific rigor of the approach to Aim 2.

Aim 2 will establish feasibility and acceptability of delivering U=U information via video in "controlled" and "clinical" settings, and will assess effects on knowledge, attitudes, and preliminary impact on ART adherence in a pilot trial. The approach is scientifically rigorous because:

- a) We will evaluate the "controlled exposure" intervention in a randomized trial, ensuring high internal validity.
- b) We will assess feasibility and acceptability of clinic-level integration of the intervention into routine HIV counseling, the delivery modality most likely to be scaled up and the approach to be tested in a future R01.
- c) We will evaluate impact with respect to theory-driven, validated measures of intervention acceptability, TasP knowledge and attitudes, HIV prevention altruism, and internalized stigma, which we will pre-test in Aim 1.
- e) We will establish feasibility of collecting data on behavioral impact through linkage to patient charts.
- f) The study is appropriately powered for a pilot trial that will establish convincing evidence of intervention acceptability and preliminary impact, which can be further tested in a larger scale trial in a future R01.

6. Data management and storage

Data with patient identifiers (i.e. names, addresses) will be stored at HE²RO on a password-protected server, as described below.

- HE2RO Server Location. Data stored by HE2RO is located on an access-controlled local server in the HE2RO office block. This server is physically secured in an access-controlled room, and only accessible virtually by designated persons with HE²RO domain login credentials.
- **HE2RO Server Details.** The HE²RO server is running the Windows Server Standard Core 2019 Operating System. As the server is the HE²RO network domain controller, Microsoft Active Directories is used to manage user accounts and folder permissions. Access to data storage folders on the server require an active HE²RO domain user account. User access to folders are decided on a case-by case basis, and limited appropriately. Remote access is controlled by means of a Virtual Private Network (using Forticlient or OpenVPN VPN software), which also requires HE²RO domain login credentials.
- **HE2RO Server Backup and Maintenance.** The server is secured and maintained by the HE²RO IT service provider, who conduct checks on server hardware and security on a regular basis, and who is also responsible for backing up the HE²RO server onsite daily, and offsite on a weekly basis.

All analyses will be conducted on fully anonymized datasets. These fully anonymized datasets will exclude all specimen and record identifiers. Instead, they will have a random study ID. The fully anonymized dataset will be made available to study staff at BU for the analyses planned in this proposal.

HE2RO will retain a linking file with data on participant identifiers (name, surname, national identification number) and TIER.Net record identifiers, which will be used in linking the questionnaire and medical records. The key linking the random study ID to the specimen and record identifiers will be held on the HE2RO password-protected server with access restricted to the PIs and server administrator. HE2RO will not have a crosswalk linking these specimen and record identifiers to patient identifying information.

7. Ethical Considerations

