5.2.1.1 Protocol Changes Occurring During the Study (text added 7/30/2025)

Our original protocol specified that after conducting the RCT (Arm A vs. Arm B), we would conduct a non-randomized clinic-level demonstration project (Arm C) with the App videos shown in clinic waiting rooms. In a protocol deviation, the first 55 participants enrolled in Arms A and B received counseling on HIV TasP/U=U from one of our enumerators during the recruitment phase and coaching on the post-test knowledge questions, regardless of study arm. This data collection error means that both intervention and control participants (Arms A and B) would have received some exposure to HIV TasP/U=U content, attenuating any impact of the intervention. It also means that our analyses of the post-test knowledge and attitudes questions must omit these 55 participants. After recognizing this error, study staff were retrained and recruitment was separated into wave 1 (n=55) and wave 2 (n=80). Following the above protocol deviation, to improve power for our primary comparison, Arm C was dropped and the planned (n=45) participants were distributed to intervention (Arm B) and control (Arm A). Our main analyses include all 135 participants in Arms A and B; in sensitivity analyses we restrict the data to Wave 2 when there was no contamination of the control group.

Our original protocol specified a six-month follow-up survey that would assess changes in patient knowledge, attitudes, and mental health over time. Due to COVID-19 related delays, we were unable to conduct the six-month follow-up survey; hence, we report only on immediate post-test knowledge and attitudes and on clinical outcomes through 10 months, extracted from patient charts. All pre-specified outcomes relying on six-month follow-up surveys were not collected and are not reported on.

Our original protocol specified "VL<50 copies/ml at 6-10 months" as the primary outcome. During the study, a change in national guidelines shifted the timing of the first VL from 6 months to 3 months after ART initiation, leading us to expand our window of observation to 3-10 months. For our primary outcome, we raised the threshold for viral suppression from VL<50 to VL<200 copies/ml, because many patients do not reach VL<50 within 3 months even if they adhere to ART and to be consistent with WHO quidelines specifying <200 copies/ml as indicating zero transmission risk. We additionally report on <50 and <1000 VL thresholds.

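### Does the leftover inverse-probability-weighting sentence in section 5.2.6 compete with the definition of the primary viral load endpoint?

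*Combined protocol and SAP*

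**What the plan says.** Section 5.2.6 lists the endpoints, including "ART uptake and adherence and viral suppression assessed in clinical records", specifies the regression models and intention-to-treat analysis, and then gives two consecutive sentences on follow-up. The first reads "Every effort will be made to follow up patients for the six-month follow-up survey". The second reads "Missingness, if >10%, will be addressed via the inverse probability of censoring weights (IPCW"). The second names neither an outcome nor a weight model.

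Section 5.2.1.1, added on 7/30/2025, explains that the six-month survey could not be run: "All pre-specified outcomes relying on six-month follow-up surveys were not collected and are not reported on". It limits reporting to the immediate post-test and to clinical outcomes through 10 months, and puts all 135 participants of Arms A and B in the main analyses. It adds: "These changes are indicated in the relevant places below in this protocol". Section 5.2.4 repeats that "Six-month survey and Arm C were dropped as described above" and describes "an immediate post-test survey conducted during the enrolment visit".

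The note at the end of section 5.2.5.4 says "Documented VL<200 copies/ml at 3-10 mo was defined as the primary endpoint". The same section makes VL monitoring, whatever the result, a secondary outcome.

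**The concern.** The weighting sentence appears to have outlived its purpose and found a new target. Once the survey is gone and the post-test is completed on the day of enrolment, only clinical-record outcomes involve follow-up that could be lost. Section 5.2.6 covers those outcomes and carries no implementation note, although sections 5.2.2, 5.2.3.2, 5.2.3.4, 5.2.4 and 5.2.5.4 each carry one. A reader who trusts the statement that changes are flagged where they occur could take the weighting rule as current and apply it to participants without a VL.

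The two treatments of such a participant answer different questions. Counting the person as not documented suppressed gives an arm credit for bringing more people onto treatment, keeping them in care and getting them tested. Treating the person as censored and reweighting those tested estimates suppression as if everyone had been tested. That removes any benefit gained through uptake or retention, which is a route the protocol's conceptual model proposes. If the plan prescribed both for the same participants, the primary result would depend on which one the analyst chose.

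**Working it through.** The documents give no figure for the share of participants without a VL, so there is no stated value to reproduce. The check has three parts.

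**1. What would be at stake if both rules applied.** Let *q* be the share of an arm with a VL in the window and *s* the share below 200 among those tested. Assume that testing is unrelated to suppression within arm.

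- Documented difference = *q*_B × *s*_B − *q*_A × *s*_A.
- Weighted difference = *s*_B − *s*_A.

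All rates below are assumed, for illustration only:

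| *q* (A, B) | *s* (A, B) | Documented difference | Weighted difference |
|---|---|---|---|
| 0.65, 0.75 | 0.85, 0.85 | 0.6375 − 0.5525 = +8.5 points | 0 |
| 0.75, 0.75 | 0.80, 0.90 | 0.675 − 0.600 = +7.5 points | +10.0 points |
| 0.80, 0.70 | 0.80, 0.90 | 0.630 − 0.640 = −1.0 point | +10.0 points |

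The two targets can differ materially. This follows from their definitions and does not show that the plan calls for both.

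**2. Whether the absence of a note makes the sentence current.** Section 5.2.6 also retains, without a note, the Arm A versus Arm C comparison, the text-message comparison in Arms B and C, and outcomes at six months. Section 5.2.5.2 still describes the six-month survey in the future tense, section 7.3 still plans contacts for it, and section 7.5 still pays for it. Sections 5.2.1.1 and 5.2.4 withdraw the survey and Arm C. Text without a local note is therefore not reliably current in this document, and section 5.2.1.1 is the controlling statement. The weighting sentence directly follows the survey sentence, and on that reading it went when the survey went.

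**3. Whether the 10% trigger can be reached on the primary endpoint.** With 135 participants, 0.10 × 135 = 13.5, so 14 missing values would be needed. Three pieces of text fix how an untested participant is classified:

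- The endpoint is documented suppression. Someone with no VL in the window has no documented value below 200.
- Monitoring is a separate outcome, so being untested is something the trial measures as a result in its own right.
- The main analyses include all 135 and follow intention-to-treat, so nobody leaves the denominator for want of a test.

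The endpoint is then a yes or no for every participant. Untested participants contribute 0 missing values (0/135 = 0%) and do not set off the rule. The medication pick-up outcome in section 5.2.5.4 is built the same way: not starting, not being retained or transferring out lowers the count and does not make it missing.

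**The case for a change.** The best case for acting is that nothing in the plan says in so many words how an absent VL is coded. Section 5.2.1.1 describes the primary outcome without the word documented, so the non-event coding is an inference. The weighting sentence is general as written, and 14 untested participants of 135 is a low bar in this setting: section 4.1.2 reports 29% of diagnosed people not on ART (100% − 71%) and under half returning for monthly pick-ups. One dated sentence would settle the matter at no cost.

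Part of this stands. The coding rule is unwritten and section 5.2.6 was not tidied. The documents also name the VL source in two ways: section 5.2.5.4 has charts plus the national laboratory database, while section 5.2.1.1 speaks of patient charts. A report should say which was used.

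The rest does not carry. The rates in section 4.1.2 come from a national household survey and from records at two Johannesburg clinics, and neither measures the absence of any VL over 3-10 months. More basically, counting untested participants towards the trigger presupposes that they are missing, which is the point in dispute and goes against the endpoint's wording.

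Read literally, the rule might also reach the post-test, from which 55 of 135 (40.7%) are omitted. That is a stated exclusion of a contaminated wave and not loss to follow-up, so weights for censoring have no role there either.

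**Conclusion.** No change to the plan is needed. The weighting sentence is a remnant of the dropped survey. The endpoint wording, the separate monitoring outcome, the all-135 analysis set and intention-to-treat together lead an analyst to one sensible coding: no documented VL below 200 at 3-10 months counts as not suppressed, with everyone in the denominator. Followed that way, the plan gives a sound primary comparison. No competing rule and no bias has been shown.

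The conclusion rests on reading documented in its ordinary sense and on treating section 5.2.1.1 as overriding un-noted text elsewhere. The differences of up to 11 points between the two approaches (−1.0 against +10.0) are hypothetical, since the documents give no VL testing rates. The protocol also states in section 5.2.8 that the pilot is not powered for effects on behaviour, so the clinical results are preliminary under either coding. Stating the coding and the VL source in the report is good practice, and any weighted or tested-only result would be shown as a labelled sensitivity analysis.
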